3. STUDY OBJECTIVES

3.1. Primary Objective

The primary objective is to assess the impact of Apremilast, compared to placebo, on Health-related Quality of Life (QOL) in subjects with manifestations of plaque psoriasis and impaired quality of life at Week 16

3.2. Secondary Objectives

The secondary objectives are:

- To assess the efficacy and safety of Apremilast compared to placebo in patients with manifestations of plaque psoriasis and impaired quality of life at Week 16
- To assess the long-term effects of Apremilast with respect to quality of life, efficacy, and safety at Weeks 32 and 52

3.3. Exploratory Objectives

The exploratory objectives are:

- To assess the efficacy of Apremilast compared to placebo in subgroups of patients with specific manifestations

4. INVESTIGATIONAL PLAN

4.1. Overall Study Design and Plan

[figure not shown]
This is a phase 4, multicenter, randomized, double-blind, placebo-controlled study of the impact of Apremilast on quality of life, efficacy, and safety in subjects with manifestations of plaque psoriasis and impaired quality of life. Approximately 276 subjects in 6-10 countries in Western Europe meeting inclusion criteria will be randomized in 2:1 ratio to receive Apremilast 30 mg BID or placebo, and to each of the stratification factors of manifestations of psoriasis (scalp psoriasis, nail psoriasis, palmoplantar psoriasis, genital psoriasis, and psoriasis in visible locations). For patients with multiple manifestations, they will be allocated to the manifestation which is most severe, as determined by the patients.

- Subjects randomized to the Apremilast treatment group will receive a 5-day titration with Apremilast followed by Apremilast 30 mg BID orally for 16 weeks. The subjects will continue with Apremilast 30 mg BID until Week 52 (i.e., a total of 52-week treatment with Apremilast). There is a dummy 5-day titration at Week 16 to maintain the blind to the original treatment assignment at randomization.
- Subjects randomized to the placebo treatment group will start with a dummy 5-day titration and receive placebo tablets (identical in appearance to the Apremilast 30 mg tablets) orally twice daily for 16 weeks. Beginning at Week 16 and after a 5-day titration with Apremilast, subjects will receive Apremilast 30 mg BID until Week 52 (i.e., a total of 36-week treatment with Apremilast).

The study consists 4 phases:

- Screening Phase – up to 5 weeks (35 days)
- Double-blind Placebo-controlled Phase – Weeks 0 through 16
Subjects will receive treatment with either
 - Apremilast 30 mg tablets orally BID, or
 - matched placebo tablets orally BID
- Apremilast Extension Phase – Weeks 16 through 52
 - All subjects will be switched to (or continue with) Apremilast 30 mg BID at Week 16 (after a 5-day titration for subjects initially randomized to placebo). All subjects will maintain this dosing through Week 52.
- Post-treatment Observational Follow-up Phase
 - 4-week post-treatment observational follow-up phase for all subjects who complete the study on treatment or discontinue from the study treatment early.

Figure 1: Overall Study Design

The study will be conducted in compliance with the International Council for Harmonization (ICH) of Technical Requirements for Registration of Pharmaceuticals for Human Use/Good Clinical Practice (GCP) and applicable regulatory requirements.

4.2. Study Endpoints

4.2.1. Primary Efficacy Endpoint(s)

The primary endpoint is achieving a ≥ 4 -point reduction from baseline in the Dermatology Life Quality Index (DLQI) at Week 16.

4.2.2. Secondary Efficacy Endpoint(s)

The secondary endpoints are

- Achieving a ≥ 4 -point reduction from baseline at weeks 32 and 52
- Change from baseline in DLQI at weeks 16, 32, and 52
- Change from baseline in Itch Numeric Rating Scale (NRS) at weeks 16, 32, and 52
- Change from baseline in Skin Discomfort/Pain Visual Analog Scale (VAS) at weeks 16, 32, and 52
- Percent change from baseline in Body Surface Area (BSA) at weeks 16, 32, and 52
- Achieving Psoriasis Area and Severity Index (PASI) score <3 at weeks 16, 32, and 52
- Achieving Patient Benefit Index (PBI) score ≥ 1 at weeks 16, 32, and 52
- Percent change from baseline in European Quality of Life 5-Dimension Questionnaire (EQ-5D) at weeks 16 and 52

Apremilast

Statistical Analysis Plan. Protocol CC-10004-PSOR-020

Amgen INC.

- Change from baseline in Work Productivity and Activity Impairment Questionnaire: Psoriasis (WPAI: PSO) at weeks 16 and 52

4.2.3. Exploratory Efficacy Endpoint(s)

The Exploratory efficacy endpoints are:

- [REDACTED]
- Achieving Static physician global assessment (sPGA) score of 0 or 1 at Weeks 16, 32, and 52 among the subjects randomized to the strata with moderate to severe psoriasis in visible areas, defined as sPGA \geq 3 at baseline, which include the dorsal hand, face, neck, or hairline.
- Achieving ScPGA score of 0 or 1 at weeks 16, 32, and 52 among the subjects randomized to the strata with moderate to severe scalp psoriasis (ScPGA \geq 3 at baseline).
- Achieving Nail Psoriasis Severity Index (NAPSI) score of 0 in the target fingernail at weeks 16, 32, and 52 among the subjects randomized to the strata with presence of nail psoriasis, defined as onycholysis and onychodystrophy in at least 2 fingernails at baseline.
- Achieving Static Physician Global Assessment-Genitalia (sPGA-G) score of 0 or 1 at weeks 16, 32, and 52 among the subjects randomized to the strata with moderate to severe genital psoriasis (sPGA-G \geq 3 at baseline).
- Achieving Palmoplantar Psoriasis Physician Global Assessment (PPPGA) score of 0 or 1 at weeks 16, 32, and 52 among the subjects randomized to the strata with moderate to severe palmoplantar psoriasis (PPPGA \geq 3 at baseline).

4.2.4. Safety Endpoints

Safety endpoints will include:

- Adverse events (AE)
- Pregnancy tests for females of child bearing potential (FCBP)
- Vital signs
- Clinical laboratory tests
- Body weight and waist circumference

4.2.5. Derivations of Efficacy Endpoints

The derivation of each efficacy endpoint is described below in separate sections. Baseline definition for all efficacy endpoints is given in [Section 5.4](#). Change from baseline is calculated as on-treatment value minus the baseline value. Percent change from baseline is defined as 100* Change from baseline/Baseline value (%). Handling of time points is described in [Section 5.5](#).

4.2.5.1. Dermatology Life Quality Index (DLQI)

The DLQI ([Finlay, 1994](#)) was developed as a simple, compact, and practical questionnaire for use in a dermatology clinical setting to assess limitations related to the impact of skin disease. The instrument contains 10 items dealing with the subject's skin. With the exception of Item Number

Apremilast**Statistical Analysis Plan. Protocol CC-10004-PSOR-020****Amgen INC.**

7, the subject responds on a four-point scale, ranging from “Very Much” (score 3) to “Not at All” or “Not relevant” (score 0). Item Number 7 is a multi-part item, the first part of which ascertains whether the subject’s skin prevented them from working or studying (Yes or No, scores 3 or 0 respectively), and if “No,” then the subject is asked how much of a problem the skin has been at work or study over the past week, with response alternatives being “A lot,” “A little,” or “Not at all” (scores 2, 1, or 0 respectively). The DLQI total score is derived by summing all item scores, which has a possible range of 0 to 30, with 30 corresponding to the worst quality of life, and 0 corresponding to the best.

If one of the 10 items are left unanswered, it is scored 0 and the scores are summed and expressed as usual out of a maximum of 30. If two or more of the ten items are left unanswered, DLQI total score will be left missing. When using sub-scales, if the answer to one item in a sub-scale is missing, the score is set to missing for that sub-scale.

4.2.5.2. Itch Numeric Rating Scale (NRS) Assessment

The Itch NRS is a single-item patient-reported outcome that asks subjects to assess the worst severity of itch over the past 24 hours and select a number on a scale of 0 to 10, where “0” represents no itching, and “10” represents the worst itch imaginable ([Naegeli, 2015](#)). The number selected by the subject will be recorded in the database.

4.2.5.3. Skin Discomfort/Pain Visual Analog Scale (VAS)

The subject will be asked to place a vertical stroke on a 100 mm VAS on which the left-hand boundary represents no skin discomfort/pain, and the right-hand boundary represents skin discomfort/pain as severe as can be imagined. The number corresponding to the stroke will be recorded in the database.

4.2.5.4. Body Surface Area (BSA)

Body surface area is a measurement of involved skin. The overall BSA affected by psoriasis is estimated based on the palm area of the subject’s hand (entire palmar surface or “handprint”), which equates to approximately 1% of total BSA.

4.2.5.5. Patient Benefit Index (PBI)

The PBI is a validated patient-reported instrument to assess patient-relevant benefits of psoriasis treatment and represents the subject benefits realized as a function of most important subject needs ([Feuerhahn, 2012](#)). PBI consist of 2 questionnaires:

- Patient Needs Questionnaire (PNQ): Prior to starting therapy, subjects are asked to assess their treatment expectations by completing the PNQ. Individual importance of treatment objectives is collected by marking the importance of a total of 25 treatment goal statements. The score ranges from 0 (no important at all) to 4 (very important) for each treatment objective will be recorded in the database.
- Patient Benefit Questionnaire (PBQ): After a period of treatment, subjects are then asked to assess the benefits of treatment by completing the PBQ with the same 25 treatment goal statements. The score ranges from 0 (not at all) to 4 (very) will be recorded in the database.

Apremilast

Statistical Analysis Plan. Protocol CC-10004-PSOR-020

Amgen INC.

A global score is calculated for each subject at a given visit by weighing the achievement values of the treatment objectives by their importance to the individual patient using the following Algorithm. Using this algorithm, the importance of each treatment goal is divided by the sum of all importance values of the respective patient and is multiplied with the goal attainment values. The resulting products are added up:

$$PBI = \sum_{i=1}^k \frac{PNQ_i}{\sum_{i=1}^k PNQ_i} PBQ_i$$

i = the ith treatment goal statement

k = total number of the applicable preference items (PNQ) and benefit items (PBQ)

For score calculation, both “does/did not apply” and “question unanswered” will be treated as missing values. The global score will be calculated using only the items pairs (i.e., importance item and benefit items) for which the patient has given a response other than “does/did not apply” in both PNQ and PBQ. For example, importance items for which the corresponding benefit item has been rated as “did not apply” (or vice versa) will not be included in the denominator within the algorithm.

4.2.5.6. Psoriasis Area and Severity Index (PASI)

The PASI is a measure of psoriatic disease severity taking into account qualitative lesion characteristics (erythema, thickness, and scaling) and degree of skin surface area involvement on defined anatomical regions. The PASI is a validated instrument that has become standard in clinical trials for psoriasis.

Psoriasis Area Severity Index scores range from 0 to 72, with higher scores reflecting greater disease severity. Erythema, thickness, and scaling are scored on a scale of 0 (none) to 4 (very severe) on 4 anatomic regions of the body: head, trunk, upper limbs, and lower limbs. Degree of involvement on each of the 4 anatomic regions is scored on a scale of 0 (no involvement) to 6 (90% to 100% involvement). The total qualitative score (sum of erythema, thickness, and scaling scores) is multiplied by the degree of involvement for each anatomic region and then multiplied by a constant. These values for each anatomic region are summed to yield the PASI score. The PASI score will be set to missing if any severity score or degree of involvement is missing. PASI scores will be presented with one digit after the decimal point.

4.2.5.7. The European Quality of Life 5-Dimension Questionnaire (EQ-5D)

EQ-5D-3L ([The EuroQol Group, 1990](#)) measures the subject's general health state as a vertical VAS and 5 quality of life domains as multiple-choice questions: mobility, self-care, main activity (work, study, housework, family/leisure activities), pain/discomfort, and anxiety/depression. The EQ-5D VAS scores range from 0 to 100, where score 0 indicates the worst imaginable health states and score 100 indicates the best imaginable health state. Using the 5-domain scores, EQ-5D index values using the UK scoring algorithm will be derived, where a higher score indicates a better health state.

4.2.5.8. The Work Productivity and Activity Impairment Questionnaire: Psoriasis (WPAI: PSO)

The WPAI: PSO questionnaire is a validated, 6-item self-administered instrument used to assess the impact of disease on work productivity in psoriasis due to specified health problem during the last 7 days. The 6 questions are: Q1 = currently employed; Q2 = hours missed due to problems associated with psoriasis; Q3 = hours missed other reasons; Q4 = hours actually worked; Q5 = degree health affected productivity while working (using a 0 to 10 Visual Analogue Scale (VAS)); Q6 = degree health affected productivity in regular unpaid activities (VAS) [Reilly, 2012] The sum of work time missed and work impairment while working yielded the overall work impairment measure. Four types of scores were calculated as following. All scores were expressed as percentages, with higher scores indicating greater impairment.

- 1) percent work time missed due to health = $Q2/(Q2 + Q4)$ for those who were currently employed;
- 2) percent impairment while working due to health = $Q5/10$ for those who were currently employed and actually worked in the past seven days;
- 3) percent overall work impairment due to health $Q2/(Q2 + Q4) + ((1 - Q2/(Q2 + Q4)) \times (Q5/10))$ for those who were currently employed. For those who missed work and did not actually work in the past seven days, the percent overall work impairment due to health will be equal to the percent work time missed due to health;
- 4) percent activity impairment due to health $Q6/10$ for all respondents.

4.2.5.9. Static Physician Global Assessment (sPGA) of visible locations

The sPGA is the assessment by the Investigator of the overall disease severity at the time of evaluation. In this study, sPGA is used to evaluate psoriasis only in visible locations, defined as dorsal hand, face, neck and hairlines.

The sPGA is a 5-point scale ranging from 0 (clear), 1 (almost clear), 2 (mild), 3 (moderate), to 4 (severe), incorporating an assessment of the severity of the three primary signs of the disease: erythema, scaling and plaque elevation. When making the assessment of overall severity, the Investigator should factor in areas that have already been cleared (i.e., have scores of 0) and not just evaluate remaining lesions for severity, i.e., the severity of each sign is averaged across all areas of visible locations, including cleared lesions.

4.2.5.10. Scalp Physician Global Assessment (ScPGA)

The ScPGA is a measurement of overall scalp involvement. The ScPGA is a 5-point scale that assesses three dimensions (Plaque Elevation, Scaling, and Erythema) on a scale of 0 (clear), 1 (almost clear), 2 (mild), 3 (moderate), to 4 (severe).

4.2.5.11. Nail Psoriasis Severity Index (NAPSI) Assessment

The number of fingers with psoriasis nail involvement, defined as onycholysis and onychodystrophy, will be counted.

Apremilast**Statistical Analysis Plan. Protocol CC-10004-PSOR-020****Amgen INC.**

The NAPSI (Rich, 2003) will assess one target thumb nail or fingernail representing the worst nail psoriasis involvement at Baseline. The total NAPSI score ranging from 0 to 8 (most severe) will be recorded in the database.

4.2.5.12. Modified Static Physician Global Assessment-Genitalia (sPGA-G)

The modified sPGA-G is the assessment by the Investigator of the overall disease severity at the time of evaluation of the genital regions. As with the sPGA, it is a 5-point scale, ranging from 0 (clear) to 4 (severe).

4.2.5.13. Palmoplantar Psoriasis Physician Global Assessment (PPPGA)

The PPPGA is the assessment by the Investigator of the overall disease severity at the time of evaluation of palms and soles ([Leonardi, 2007](#)). The scale ranges from 0 (clear) to 4 (severe).

4.3. Stratification, Randomization, and Blinding

Randomization is carried out using an Interactive Voice Response System (IVRS). Treatment assignment is following a 2:1 ratio between Apremilast 30 mg BID arm and placebo arm. Randomization method is based on permuted-block randomization. Subjects were targeted to be randomized within each of the 5 manifestations of plaque psoriasis (i.e., scalp psoriasis, nail psoriasis, palmoplantar psoriasis, genital psoriasis, and psoriasis in visible locations). If subjects present with multiple manifestations, they will be allocated to the manifestation which is most severe, as determined by the subject.

Data analysis and reporting will be performed for publication after all subjects have completed the double-blind placebo-controlled phase at Week 16/Visit 5 or have discontinued early. A copy of the 16-week data extraction will be transferred for analysis after medical/scientific review has been completed, protocol violations/deviations have been identified, and the data have been declared cleaned. Selected members of the study team and external partner who do not have direct interaction with subjects are unblinded for the analysis of the Week 16 data. These persons may include but are not limited to the following: Therapeutic Area Head, Study lead, Medical Director and the Statistician. The results from these analyses may be published prior to the end of the study.

Subjects, Investigators and persons responsible for the ongoing conduct of the study will continue to be blinded to the original treatment assignment until the 52-week database lock at end of the study. These persons are those individuals who have direct interaction with subjects and/or subject assessments and may include but are not limited to the following: Clinical Trial Manager, Data Manager, Clinical Research Associates and Site Monitors.

For the purpose of the data analyses supporting the CSR after all subjects have completed the post-treatment observational follow-up or have discontinued early, the 52-week database will be locked after medical/scientific review has been performed, protocol violations/deviations have been identified, and the data have been declared final and complete.

4.4. Sample Size Determination

For the primary endpoint, i.e., the response rate (π) defined as the proportion of subjects achieving a ≥ 4 -point reduction from baseline in DLQI at Week 16, the superiority of Apremilast 30 mg BID versus placebo will be tested. The hypotheses on superiority are defined as:

$$H_0: \pi_{APR} - \pi_{PBO} = 0$$

versus

$$H_1: \pi_{APR} - \pi_{PBO} > 0$$

Using an exploratory analysis on a subset of subjects meeting the following criteria: a) ScPGA ≥ 3 or b) NAPSI ≥ 1 or c) PPPGA ≥ 3 at baseline and DLQI ≥ 10 at baseline in the PSOR-008 and PSOR-009 Phase 3 studies, it was estimated that the proportion of subjects who achieved a ≥ 4 -point reduction from baseline in DLQI was 0.50 (97 responders out of 193 subjects) and 0.83 (337 responders out of 406 subjects) for placebo and Apremilast 30 mg BID, respectively.

Assuming a placebo DLQI responder proportion of 0.50 at Week 16, a minimum total sample size of 210 subjects (140 allocated to Apremilast 30 mg and 70 allocated to placebo) is needed to detect a 0.20 difference in the DLQI responder rate between Apremilast and placebo with at least 0.807 power using a two-sided test at the 0.05 level of significance. This sample size calculation is based on an unpooled variance, and determined using the commercial software EaST, Version 6.3. Allowing for an 24% discontinuation rate prior to Week 16, the sample size of 276 subjects should be sufficient.

5. GENERAL STATISTICAL CONSIDERATIONS**5.1. Reporting Conventions**

- The statistical test on the primary endpoint is at a 2-sided 0.05 significance level, any p-values reported for other endpoints are considered as summary statistics;
- P-values are rounded to 4 decimal places. P-values that round to 0.0000 are presented as '<0.0001' and p-values that round to 1.000 are presented as '>0.9999';
- Confidence intervals (CIs) are presented as 2-sided 95% CIs;
- Summary statistics consist of the number and percentage of subjects in each category for discrete variables, and the sample size, mean, median, Standard Deviation (STDEV), minimum, and maximum for continuous variables;
- All mean and median values are formatted to one more decimal place than the measured value, standard deviation values are formatted to two more decimal places than the measured value, minimum and maximum values are presented to the same number of decimal places as the measured value, and the 95% CI are formatted to two more decimal places than the measured value;
- All percentages are rounded to one decimal place. The number and percentage of responses are presented in the form XX (XX.X), where the percentage is in the parentheses, and the 95% CI are presented to two decimal places. Exact 100% that is not rounded from a percent >99.50% is presented in the format xx (100);
- All listings are sorted for presentation in order of treatment arm, study center, subject, and date of procedure or event;
- All analysis and summary tables have the analysis population sample size (i.e., number of subjects);
- All laboratory data will be reported using standard international (SI) units.

5.2. Analysis Phases or Periods

Data summary and analysis will be provided for the following analysis phases/periods.

5.2.1. Placebo-controlled Phase – Weeks 0 to16

The Placebo-controlled phase is per protocol specification. All the efficacy and safety analyses for the primary time point at Week 16 are based on placebo-controlled phase, including data collected from Day 1 for the core baseline (defined in Section 5.4). The end date is defined as following:

- (1) One day prior to the first dose date of Apremilast dispensed at Week 16/Visit 5 for patients who are entering the Apremilast Extension Phase;
- (2) the day of the discontinuation visit if the subject discontinued prior to or at Week 16/Visit 5;

Apremilast

Statistical Analysis Plan. Protocol CC-10004-PSOR-020

Amgen INC.

- (3) the last known study day if the subject is lost to follow-up prior to Week 16/Visit 5.

All by-treatment tabulations based on the data from Placebo-controlled Phase are grouped by Apremilast 30 mg BID vs. placebo.

5.2.2. Apremilast Extension Phase – Weeks 16 to 52

The Apremilast Extension Phase is per protocol specification. Quality of life and efficacy endpoints, patient disposition, protocol deviation/violation, and study treatment compliance are summarized based on data from this study phase.

The Apremilast Extension Phase starts on the day that the first dose of treatment is dispensed for the phase at Week 16/visit 5 and the end date is defined as the following:

- (1) the day of Week 52/Visit 9 for patients who complete the study on treatment;
- (2) the day of the discontinuation visit if the subject discontinued prior to or at Week 52/Visit 9;
- (3) the last known study day if the subject is lost to follow-up prior to Week 52/Visit 9.

All by-treatment tabulations are grouped by Apremilast 30 mg BID arm vs. placebo arm, i.e., the original treatment during the placebo-controlled phase.

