5.5. Time Points

Time points in all analyses are based on the visits/study weeks using the following visit mapping algorithm, which may or may not be the same as the visits/study weeks as recorded in the database.

Post baseline time points in all analyses will be captured based on analysis visit window (range of study days) around the target day for each analysis visit, based on the actual day of evaluation relative to a reference date. Appropriate dates will be used to calculate the study day, e.g., date of measurement or date of specimen collection will first be used, and then the date of visits/study weeks as recorded in the database will be used. If there are multiple measurements within a time point based on the study day, then the non-missing value from the closest measurement to the planned study day will be used for that visit. If the value at a scheduled visit is missing and there is no value available within the time window based on the study day, the value at the study week will be missing.

Table 2: Table for Visit Mapping for by Time Point Analysis

Analysis Visit	Target Day	Visit Window
Baseline	1	≤ 1
Placebo-controlled Phase (for all endpoints)		
Week 2	15	2 – 21
Week 4	29	22 – 70
Week 16	113	71 – End of Placebo-controlled Phase
Apremilast Extension Phase (for efficacy endpoints)		
Week 20	141	Start of Apremilast Extension Phase – 182
Week 32	225	183 – 294
Week 52	365	295 – End of Apremilast Extension Phase
Apremilast Extension Phase (for safety endpoints)		

Apremilast

Statistical Analysis Plan. Protocol CC-10004-PSOR-020

Amgen INC.

Week 20	141	Start of Apremilast Extension Phase – 182
Week 32	225	183 – 266
Week 44	309	267 – 337
Week 52	365	338 – End of Apremilast Extension Phase

Note: Target day and visit window are relative to the date of Visit 2/Week 0 (Day 1) for randomization. Definitions for baseline and start or end of the phases are specified in [Section 5.25.2](#) and [5.4](#) for both efficacy and safety analysis.

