Time points in the analyses or summaries of efficacy data over time include the scheduled study weeks per protocol, the end of a study phase, and the observational follow-up visit. Appropriate dates (e.g., date of measurement or date of specimen collection) will first be used to ensure only data (including data from scheduled, unscheduled, container visits, discontinuation, and observational follow-up visits) measured or collected within the specific analysis phase (as defined in Section 5.2) being analyzed or summarized are included, and then the visits/study weeks as recorded in the database will be used to assign one value (possibly missing) to each time point at the subject level. It is possible that multiple assessment values will fall into the same visit window. The following rule may be used to select the unique value for that analysis visit:

1. Among all assessments in the same visit window for the analysis visit, select the value with the assessment date closest to the target day of the analysis visit;
2. If the relative days from 2 assessments are equally close to, but on different sides of the target day, then the latter assessment will be used for that analysis visit;
3. If multiple assessments are available on the same relative day, then the highest value of these assessments will be used for that relative day.

The time points for summaries of safety data (laboratory parameters, vital signs and weight) are based on study week/visit for the placebo-controlled phase. For the Apremilast Exposure Period, the scheduled study weeks for placebo subjects who are treated with Apremilast 30 mg BID at Week 16 will be mapped to reflect the study weeks relative to the first dose of Apremilast (see table below).

Table 3: Adjustment and Mapping of Study Weeks for Placebo Subjects who are Treated with Apremilast 30 mg BID after Week 16 in Summary of Safety Data over Time

Original Visit	Re-Mapped Visit for subjects initially randomized to placebo
Week 16	Baseline
Week 20	Week 4
Week 32	Week 16
Week 44	Week 28
Week 52	Week 36

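### The SAP's date rules push a pre-dose Week 16 DLQI out of the Week 16 window when the first extension dose is taken on the Visit 5 date

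*SAP*

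**What the plan says.** - **Phase end (SAP 5.2.1, item 1).** For extension entrants the Placebo-controlled Phase ends "One day prior to the first dose date of Apremilast dispensed at Week 16/Visit 5 for patients who are entering the Apremilast Extension Phase".
- **Extension start (SAP 5.2.2).** "The Apremilast Extension Phase starts on the day that the first dose of treatment is dispensed for the phase at Week 16/visit 5".
- **Week 16 window (SAP 5.5, Table 2).** Target Day 113, window "71 – End of Placebo-controlled Phase". The Week 20 window, target Day 141, runs from the start of the extension to Day 182.
- **Order of operations (SAP 5.5).** Analysis visits follow a mapping "which may or may not be the same as the visits/study weeks as recorded in the database". For efficacy over time, dates are applied first "to ensure only data (including data from scheduled, unscheduled, container visits, discontinuation, and observational follow-up visits) measured or collected within the specific analysis phase" are included, "and then the visits/study weeks as recorded in the database will be used to assign one value (possibly missing) to each time point".
- **When a week is missing (SAP 5.5).** The sentence that sets a study week to missing begins "If the value at a scheduled visit is missing and there is no value available within the time window based on the study day".
- **Visit procedure (protocol 6.2).** Evaluations come before dosing on the visit day unless stated otherwise. Protocol 6.4.1 has the DLQI completed on arrival, before anything else.
- **Contrast (SAP 5.4).** The apremilast safety baseline accepts a value from the day of the first apremilast dose itself.

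**The concern.** A Visit 5 DLQI taken before the first extension dose is a valid placebo-controlled measurement. If the dose follows on the same day, the one-day-earlier phase end removes it from the phase, and Table 2 then removes it from Week 16. The same happens to BSA, PASI, itch NRS, pain VAS and PBI. No visit is scheduled between Weeks 4 and 16 (protocol 3.2), so normally only an unscheduled assessment from Day 71 could fill the gap.

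The affected subject's primary outcome would be imputed from baseline, Week 2 and Week 4 scores. In the supportive analyses it would usually become the Week 4 value (LOCF) or a non-response (NRI). The SAP is also uneven: item 2 of 5.2.1 keeps the discontinuation-visit day, so a subject who discontinues at Visit 5 keeps that day's score while a completer who doses that day loses it.

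SAP 5.2.2 has a related fault that does not depend on who doses when. It starts the extension on the dispensing day, which is the Visit 5 date, so Visit 5 is never in the placebo phase alone.

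**Working it through.** **1. Boundary check.** Rules: placebo phase end = first extension dose day − 1; extension start = Visit 5 day; Week 16 = Day 71 to phase end. Take Visit 5 on Day 113.

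| First extension dose | Phase ends | Extension starts | Visit 5 lies in | Overlap |
|---|---|---|---|---|
| Day 113 | Day 112 | Day 113 | extension only | 0 days |
| Day 114 | Day 113 | Day 113 | both | 1 day |
| Day 115 | Day 114 | Day 113 | both | 2 days |

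In the first row the target day itself is outside the Week 16 window (Days 71–112) and inside the Week 20 window (Days 113–182). Visits on Days 109, 110, 116 and 117 with same-day dosing give the same result. Within the Week 20 window, Visit 5 is 141 − 113 = 28 days from target, so a Week 20 visit within its ±4 days displaces it. Without a Week 20 visit, Visit 5 can stand as Week 20, and a placebo subject's pre-apremilast score would be shown as an on-apremilast value.

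**2. The plan's own power figure.** SAP 4.4: 0.70 versus 0.50, 140:70, two-sided 0.05, stated power 0.807. With unpooled variance, power = Φ(0.20/√(0.21/n₁ + 0.25/n₂) − 1.96). At 140/70 this is Φ(0.20/0.0712 − 1.96) = 0.802. The pooled form gives 0.807. The protocol's 0.872 at 170/85 is also reproduced (0.872). The stated figures hold.

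**3. Size under an assumed same-day share f.** The documents give no f. SAP 15.3 assumes intake from a new card on the dispensing date, but only for counting tablets, so it is not evidence of the actual share.

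- Subjects reaching Visit 5: 276 × 0.76 = 209.8, about 210 (SAP 4.4). All are assumed to enter the extension with no other assessment from Day 71.
- Values excluded = 210 × f.
- Missing at Week 16 = (276 − remaining)/276.
- NRI difference = 0.20 × 0.76 × (1 − f), taking the design rates to hold among completers.

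| f | Excluded | Missing at Week 16 | Observed n (apremilast/placebo) | Observed-data power | NRI difference |
|---|---|---|---|---|---|
| 0% | 0 | 66/276 = 24% | 140/70 | 0.802 | 0.152 |
| 10% | 21 | 87/276 = 32% | 126/63 | 0.759 | 0.137 |
| 25% | about 52 | 118/276 = 43% | 105/53 | 0.684 | 0.114 |
| 50% | 105 | 171/276 = 62% | 70/35 | 0.510 | 0.076 |

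The fall from 0.20 to 0.152 at f = 0 is ordinary dropout. Only the further fall comes from this rule.

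**4. Allowing for imputation.** Observed-data power is the worst case, in which imputation recovers nothing. A simulation used 140/70 subjects, a normal latent score with one earlier-visit predictor, exclusion completely at random, normal-regression imputation with M = 25, dichotomising, Rubin's rules and 2,000 runs. For assumed correlations of 0, 0.3, 0.5 and 0.7 between the earlier and Week 16 scores, power was:

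- f = 25%: 0.71, 0.70, 0.72, 0.74
- f = 50%: 0.53, 0.55, 0.58, 0.63

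Monte Carlo error is about 0.01. Predictive mean matching with K = 5, closer to the SAP's method, gave similar values.

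**The case against.** The best defence is that the SAP supports the intended reading in several places. SAP 5.2.1 opens by tying the phase to the protocol, whose Table of Events puts Week 16 in the placebo-controlled part. SAP 4.3 treats Visit 5 as completing that phase. The sentence that sets a week to missing also requires the scheduled value to be missing, and here it is observed. SAP 9.3 imputes only missing scores. A sensible programmer would use the nominal visit.

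The intent is indeed clear, and the missing-value sentence does not by itself cause the exclusion. But 5.2.1 goes on to give an explicit end date, and 5.5 invokes that definition and applies it before the recorded visit. Using the nominal visit would depart from the stated order for the primary endpoint.

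Two further points are fair. The power figures need both literal programming and an assumed share. And Week 20 is not a named endpoint and is only summarised descriptively, so the Week 20 misplacement is minor.

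On the remedy, drug dispensed at Visit 5 cannot be taken before Visit 5, so a later-of-two-dates rule usually reduces to the dose date. It still covers a subject who is dispensed drug but never doses.

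**Conclusion.** The concern holds. As written, 5.2.1(1), Table 2 and the date-first step in 5.5 exclude a pre-dose Visit 5 assessment from Week 16 whenever the first extension dose is taken that day, and 5.2.2 places Visit 5 in the extension in every case. This is a drafting error, not a design choice. Confidence is high on the boundary arithmetic; the size is unknown because the same-day share is not documented. It is nil at 0%. At 25%, power lies between 0.68 (observed data only) and about 0.74; at 50%, between 0.51 and about 0.63, under the assumptions shown.

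The rule applies to both arms, so the expected cost is lost precision and a diluted NRI difference, not a tilt toward one arm. Subjects who discontinue, who first dose on a later day, or who have another assessment from Day 71 keep a Week 16 value. The primary analyses of EQ-5D and WPAI use the scheduled Week 16 visit and are not affected. It should be corrected because it concerns the primary-endpoint window.

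**What to change.** - **SAP 5.2.1(1) and Table 2:** for efficacy assessments of extension entrants, end the Placebo-controlled Phase on the later of the Visit 5 date and the first extension dose date. Count pre-dose assessments on that date, in line with the same-day convention in 5.4. Where no time is recorded, treat the assessment as pre-dose, as protocol 6.2 expects.
- **SAP 5.2.2 and Table 2:** start the extension efficacy windows the day after that date, in place of the dispensing day. In the three boundary cases the placebo phase then ends on Days 113, 114 and 115, the extension starts on Days 114, 115 and 116, and there is no overlap.
- **Adverse events:** keep the day-before-dose cut.
- **Laboratory and vital-sign data:** Table 2 applies its placebo-phase windows to every endpoint, while the text of 5.5 assigns these data by study week or visit. Reconcile the two.

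The cost is a few words in 5.2.1, 5.2.2, 5.5 and Table 2, plus programming. No new data or treatment information is needed. SAP section 2 plans signature before the Week 16 data transfer, so the change should be made before that transfer.
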